2.10 PD and PK/PD analyses

PK concentration and B-cell count data will be summarized by visit for the overall population, and separately by region (Japan or non-Japan) and provided together with by-patient listings in the study report. All patients in FAS with non-missing values will be included in these analyses.

[figure not shown]

[figure not shown]
2.11 Immunogenicity assessment

Samples will be analyzed for the presence of human anti-drug antibodies (ADA). The proportion of patients with ADA will be summarized by visit window and overall (i.e. proportion of patients with ADA) as an assessment of the immunogenicity potential of ofatumumab. A listing by patient will also be provided. All patients in FAS with non-missing values will be included.

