Ofatumumab is a human anti-CD20 monoclonal antibody (mAb) approved for the treatment of patients with chronic lymphocytic leukemia (CLL) (Arzerra®). The actions of ofatumumab on B-cells are similar to rituximab and ocrelizumab. Ofatumumab recognizes a unique epitope localized close to the cell membrane on the 2 extracellular domains of the CD20⁺ molecule, N-proximal of the epitope for the anti-CD20 mAb rituximab. CD20-binding of ofatumumab induces B-cell lysis primarily through complement-dependent cytotoxicity (CDC) and antibody-dependent cell-mediated cytotoxicity (ADCC). As a fully human antibody, ofatumumab is predicted to have low potential for immunogenicity, as confirmed by the very low incidence of anti-drug antibodies (ADA) against ofatumumab observed in clinical studies (<1% of patients in oncology studies, [Arzerra® US prescribing information](#)).

Ofatumumab has been evaluated in two Phase 2 studies in patients with RRMS (Studies OMS115102 and OMS112831). Study OMS115102 was a 48-week (24-week cross-over), double-blind, placebo-controlled study that evaluated the effects of ofatumumab administered iv in 38 patients with RRMS ([Soerensen et al 2014](#)). The study consisted of 3 dose cohorts (100 mg, 300 mg, 700 mg) with 12 patients randomized in each cohort to ofatumumab or placebo in a 2:1 ratio. After 24 weeks, patients on ofatumumab were switched to placebo and patients on placebo were switched to the ofatumumab dose of their cohort and followed for 24 weeks (Week 24-48). The study showed that iv administration of ofatumumab resulted in a profound reduction in circulating B-cell counts and suppression of MRI lesion activity at each dose level evaluated in both treatment periods (Week 0-24 and Week 24-48).

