Visit		SCR (D-45 to D-8)	BL (D-7 to D1 (pre-treatment)	D1 ¹	D2	D5	D7	D14	W4 (D28)	W8	W12	W16	W20	W24		W25 ¹⁹	W26 ¹⁹	W28	W36	W48	W60 ²⁰	W72 ²⁰
Visit No.	1	20	110	120	130	140	150	160	170	180	190	200	210	220	230	240	250	260	270	280	1999	
Visit Window (days)	n.a.	n.a.	n.a.	0	-1	±1	±1	±3	±7	±7	±7	±7	±7	±1	±1	±3	±7	±7	±14	±14	n.a.	
Contraception status ¹¹	X	X						X	X	X	X	X	X			X	X	X	X	X	X	
PK sampling ¹²		X		X	X	X	X	X		X			X			X	X	X	X	X	X	
ADA sampling ¹²		X						X		X			X			X	X	X	X	X	X	
Total IgM, IgG levels	X ^{9a}	X ^{9a}						X		X			X			X	X	X	X	X	X	
Serological markers for hepatitis A, B, C, and E	X												X									
HIV test	X																					
MRI ¹³	X									X	X	X	X				X	X			X ¹⁴	
EDSS	X	X ^{9b}	X ^{9b}						X		X						X	X	X	X	X	
eCSSRS	X ^{9a}	X ^{9a}	X	X	X	X	X	X	X	X	X	X	X	X	X	X	X	X	X	X	X	
AEs	X	X	X	X	X	X	X	X	X	X	X	X	X	X	X	X	X	X	X	X	X	
MS Relapse	X	X	X	X	X	X	X	X	X	X	X	X	X	X	X	X	X	X	X	X	X	
Prior/Con Meds ¹⁵	X	X	X	X	X	X	X	X	X	X	X	X	X	X	X	X	X	X	X	X	X	
Phone interview ¹⁶															X	X	monthly between planned visits					
Patient diary review															X	X	X	X	X	X	X	
Disposition														X								X

A/A=Acetaminophen/Antihistamine; ADA=Anti-drug-antibody; AEs=Averse events; BL=baseline; Con meds=Concomitant medications; D=day; Excl.=exclusion; Incl.=inclusion; n.a.=not applicable; S= Steroid; SCR=screening; W=week.

1. Randomization and first dose (usually expected on the same day). If first dose occurs on a different day after randomization, the day of first dose should be considered to be Day 1. Patients must remain at the site under observation for a minimum of 5 hours following dosing on Day 1.
2. EOS visit will be required for all patients (Patients who permanently discontinue study drug and patients who complete the study).
3. Syphilis and Tuberculosis testing must be done as part of eligibility check (Exclusion criterion #9) unless completed in the last 6 months prior to screening with documented negative results. For syphilis testing, it should be done per local clinical practice (e.g. by positive RPR). For tuberculosis testing, QuantiFERON®-TB Gold test will be done by the central laboratory to assess patient's eligibility at Screening.
4. All assessments required for the Core part MUST be completed before the patient receives the first dose for the Extension part at Week 24. Patients must remain at the site under observation for a minimum of 5 hours following dosing at Week 24.

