6.6.2 Immunogenicity

ADA will be assessed to evaluate the immunogenicity potential of ofatumumab. Sampling time points are provided in [Table 6-1](#). Samples for ADA assessment should be taken prior to dosing at the visit. For ADA visits after Week 36, if the visit coincides with the day the monthly injection is scheduled, the patient should not take the injection in the morning before coming to the site so that the ADA sample can be drawn before the injection. The ADA sample collection date and time must be entered on the appropriate CRF.

[REDACTED]

7 Safety monitoring

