9.5.5 Immunogenicity assessment

Samples will be analyzed for the presence of human anti-drug antibodies (ADA). The proportion of patients with ADA will be summarized by visit and overall (i.e. proportion of patients with ADA) as an assessment of the immunogenicity potential of ofatumumab. A listing by patient will also be provided.

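### The ADA summary makes no use of the pre-dose sample, so patients already antibody-positive before their first ofatumumab dose can be counted in the assessment of its immunogenicity

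*SAP*

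**What the plan says.** Protocol 6.6.2 gives the purpose: "ADA will be assessed to evaluate the immunogenicity potential of ofatumumab". It also fixes the timing: "Samples for ADA assessment should be taken prior to dosing at the visit". Table 6-1 of the protocol schedules the first ADA sample at the Baseline visit (Day -7 to Day 1, before treatment), then at Weeks 4, 12, 24, 28, 36, 48 and later visits.

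Protocol 9.5.5 defines the summary: "The proportion of patients with ADA will be summarized by visit and overall (i.e. proportion of patients with ADA"). SAP 2.11 keeps this measure and replaces visit by visit window: "The proportion of patients with ADA will be summarized by visit window and overall (i.e. proportion of patients with ADA"). It offers the figure "as an assessment of the immunogenicity potential of ofatumumab" and adds a by-patient listing. The SAP's population is broad: "All patients in FAS with non-missing values will be included". The FAS contains both randomized arms, and the placebo arm receives no ofatumumab before Week 24.

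The window rules that govern ADA are in SAP 2.1.2. In Table 2-3 the first ADA window is Week 4, Day 1 to Day 56, and there is no baseline row. Days count from the first Core dose at Cut-off 1, and from the first ofatumumab dose at Cut-off 2 and the final analysis. Where a qualitative variable has several records in one window, SAP 2.1.2.3 takes the worst.

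**The concern.** Immunogenicity of a drug means antibodies that appear, or rise, after exposure to it. A plain proportion positive mixes these with antibodies or reactivity present beforehand. The reference sample that separates the two is collected, but no rule in either document connects it to the result: there is no definition of treatment-emergent ADA and no cross-classification by baseline status. Nor does the SAP say whether the overall figure covers post-baseline samples only.

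The SAP applies the before-and-after principle elsewhere: treatment-emergent adverse events (2.8.1), new or worsening laboratory abnormalities (2.8.3), newly occurring liver and renal events (5.3.2, 5.3.3), and emergence of suicidal behavior against prior history (2.8.4.3).

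At stake is whether the reported ADA rate can be read as an effect of ofatumumab. Few positives are expected, as protocol 1.1 refers to a "very low incidence of anti-drug antibodies (ADA) against ofatumumab observed in clinical studies", so a single misattributed patient could determine the published percentage in a study intended to support registration in Japan.

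**Working it through.** The documents state no expected ADA rate, precision or power for this trial, so there is no planned figure to reproduce. The check has two parts: which samples count under the written rules, and how much one patient moves the result.

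**Which samples count**

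1. *Positive at Baseline and at later visits.* The later samples fall in the Week 4, 12 and 24 windows and onward. The patient is positive in each window and overall, whether or not the overall figure includes the baseline sample. This follows directly from SAP 2.11.
2. *Pre-dose sample on the first-dose day.* Under SAP 2.1.1 the first-dose date is Day 1 and there is no Day 0. Day 1 opens the Week 4 window. ADA presence is qualitative, so if positive is the worst record (2.11 does not say), a positive pre-dose sample would override a negative Week 4 sample under 2.1.2.3. SAP 2.1.1 takes as baseline the latest value up to and including the first-dose date, and 2.1.2 says baseline needs no window. That probably removes the sample, but no sentence says that a value used as baseline is withheld from the windows.
3. *Week 24 pre-dose sample of placebo-to-ofatumumab patients, Cut-off 2 and final.* If drawn on the dosing day it is again Day 1. The switcher-specific baseline in 2.1.1 is written for safety analyses. ADA sits in its own section on the FAS, outside 2.8, so whether that clause applies is unclear. For vital signs, Table 2-8 expressly keeps Week 24 data from being re-mapped; Table 2-3 has no such note for ADA.
4. *Earlier Core samples of those patients, Cut-off 2 and final.* Counted from the first ofatumumab dose, these have negative days and fall in no window. The overall figure does not say that they are excluded.

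**Size**

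Inputs: 60 patients randomized 2:1 (SAP Section 3), so 60 × 2/3 = 40 on ofatumumab; incidence under 1% in oncology studies (protocol 1.1); baseline reactivity *b*, not in the documents and therefore assumed.

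- One patient: 1/40 = 2.5 percentage points. If the arms were pooled (2.11 does not state a split by treatment), 1/60 = 1.7 points.
- Chance of at least one baseline-reactive patient among 40: 1 − (1 − *b*)^40.

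| Assumed *b* | Chance of at least one of 40 |
|---|---|
| 0.1% | 1 − 0.999^40 = 4% |
| 0.5% | 1 − 0.995^40 = 18% |
| 1% | 1 − 0.99^40 = 33% |
| 2.5% | 1 − 0.975^40 = 64% |
| 5% | 1 − 0.95^40 = 87% |

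- Expected reading of the plain proportion in the ofatumumab arm, taking a true treatment-emergent rate *t* = 1% among baseline-negative patients and every baseline-reactive patient counted: *b* + (1 − *b*)*t*. For *b* = 0, 1%, 2% and 5% this is 1.0%, 2.0%, 3.0% and 6.0% (rounded). A treatment-emergent proportion among baseline-negative patients stays at 1.0% throughout.

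**The case against.** The strongest reply is that little can go wrong in practice. SAP 2.11 offers the proportion as one assessment, and the same section requires a by-patient listing. With about 60 patients and few positives, a reader can inspect each positive patient's sequence of samples. The placebo patients in the FAS would also show background reactivity at Cut-off 1. The result is descriptive and untested. All of this is fair and limits the importance of the point. It does not correct the summary percentage, which is what readers will cite, and 2.11 does not state that ADA is shown by arm.

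Four stronger readings are tempting, and the documents do not support them.

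- *Every Core-part positive of a switcher is counted by window as an ofatumumab positive.* At Cut-off 2 and final, Table 2-3 counts from the first ofatumumab dose, so samples before that date have no window. Only the same-day Week 24 sample and the undefined overall figure remain open.
- *A patient positive only at Baseline is counted overall.* This is a possible reading, but baseline has no window and the overall figure most naturally runs across the windows.
- *A spurious regional ADA difference would be reported.* SAP 2.11 plans no regional ADA summary. SAP 2.10 plans regional summaries for PK and B-cell counts. Only the general subgroup provision in 2.1 could bring one in.
- *Assay reactivity will inflate the rate.* The assay and its confirmatory steps are not described, so this remains a possibility.

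The comparison with the cited rate under 1% also needs care, because protocol 1.1 does not say whether that rate is treatment-emergent.

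**Conclusion.** The concern holds in limited form. As written, the ADA result counts patients who were positive before their first ofatumumab dose and remained so, and the Day 1 start of the Week 4 window leaves a same-day pre-dose sample open to being counted as post-dose. Each such patient adds 2.5 points among 40.

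How likely this is cannot be settled from the documents. The range of 4% to 87% rests wholly on assumed baseline reactivity of 0.1% to 5%. With no baseline reactivity the chance is nil. The figures are upper bounds if only patients who stay positive are counted. A reader might infer that a false immunogenicity signal is probable, or that efficacy conclusions are affected. Neither follows: no baseline rate is given, and the ADA summary plays no part in the primary test. This is a gap in how the result is defined, since the data needed to close it are already collected.

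**What to change.** In SAP 2.11:

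- Make treatment-emergent ADA the main figure, by treatment group: negative in the last sample before the first ofatumumab dose (Day 1, or Week 24 for placebo-to-ofatumumab patients) and positive in at least one later sample.
- Use as denominator ofatumumab-treated patients with a pre-dose sample and at least one post-dose sample.
- Report baseline prevalence, and the later course of baseline-positive patients, on a separate line. Add boosted ADA only if titres are available; the SAP mentions analysis for presence only.
- State that pre-dose samples, including those drawn on the first-dose day, are excluded from the post-baseline windows and from the overall figure.

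The cost is SAP wording and a derived flag on samples already scheduled. The one small drawback is that patients without a pre-dose sample leave the denominator; their number should be shown.

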2.12 Patient-reported outcomes

Not applicable.

2.15 Analysis on the Extension part not mentioned in the previous sections

Switch effect from placebo to ofatumumab on the number of Gd-enhancing T1 lesions

Mean numbers of Gd-enhancing T1 lesions per scan, defined as

$(\text{total number of Gd-enhancing T1 lesions}) / (\text{total number of scans}),$

will be calculated by treatment and study period (up to Week 24, or thereafter).

Also, mean numbers of Gd-enhancing T1 lesions per scan will be summarized by region and study period.

In addition, mean numbers of Gd-enhancing T1 lesions per scan will be summarized by subgroup of home injection and study period.

Switch effect from placebo to ofatumumab on the number of new or enlarging T2 lesions

Annualized rate of new or enlarging T2 lesions, defined as

$(\text{total number of new or enlarging T2 lesions}) / (\text{total time of MRI assessment}),$

will be calculated by treatment and study period (up to Week 24, or thereafter).

For this calculation, each patient's number of new or enlarging T2 lesions will be relative to Week 24. In addition, definition of time of MRI assessment will depend on the study part:

- For the period up to Week 24, the time of MRI assessment will be defined as $(\text{Week 24 visit date}) - (\text{first dose date in the Core part}) + 1$ divided by 365.25.
- For the period after Week 24, the time of MRI assessment will be defined as $(\text{Week 48 visit date}) - (\text{Week 24 visit date})$ divided by 365.25. If Week 48 visit is not available, the time of MRI assessment will be defined as $(\text{last visit date up to Week 48}) - (\text{Week 24 visit date})$ divided by 365.25.

Switch effect from placebo to ofatumumab on the annualized relapse rate (ARR)

ARR (time-based and patient-based) will be summarized by study period (up to Week 24 or thereafter).

Here definition of time in study will depend on the study part:

- For the period up to Week 24, the time in study will be defined as (Week 24 visit date) – (first dose date in the Core part) + 1 divided by 365.25.
- For the period after Week 24, the time in study will be defined as (last visit date up to date of Cut-off 2) – (Week 24 visit date) divided by 365.25.

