2.1.1 General definitions

Study drug/treatment refers to the investigational drug Ofatumumab and placebo.

“Date of Cut-off 2” is expected as the date the last patient completes all assessments at Week 48 visit. If the last patient discontinues from the study prior to Week 48 visit, “date of Cut-off 2” is the last patient's last visit.

Date of first administration of study drug/treatment, or first date of study drug/treatment, is defined depending on the analysis purposes.

- For Cut-off 1 analysis and Cut-off 2 and final *efficacy* analysis, it refers to the date when the first dose of randomized treatment is administered.
- For Cut-off 2 and final *safety* analysis, it refers to the date when the first dose of ofatumumab is administered.

Date of last administration of study drug/treatment, or last date of study drug/treatment is defined by analysis time point.

- For Cut-off 1 analysis, it refers to the date when the last dose of randomized treatment is administered up to Week 24 visit.
- For Cut-off 2 analysis, it refers to the date when the last dose of treatment is administered up to the date of Cut-off 2.
- For final analysis, it refers to the date when the last dose of treatment is administered up to EOS visit.

Study day is defined as: if after first date of study drug, then (Study Day) = (Date) – (first date of study drug) +1; if before first date of study drug, then (Study Day) = (Date) – (first date of study drug); Study Day 1 is defined as the date of the first administration of study drug; there is no Study Day 0.

Duration of an event is calculated as (event end date) – (event start date) +1.

1 month is counted as 30 days unless otherwise specified.

Baseline is defined for each cut-off analysis.

- For Cut-off 1 analysis, and Cut-off 2 and final *efficacy* analysis, baseline is defined as the last non-missing result before or on the first date of study drug.
- For Cut-off 2 and final *safety* analysis, definition of baseline depends on each patient's treatment course in the study
 - For a patient continuously having ofatumumab across Core and Extension parts, baseline is defined as the last non-missing result before or on the first date of study drug.
 - For a patient switching the treatment from placebo to ofatumumab when entering the Extension part, baseline is defined as the dose date of ofatumumab at Week 24. *For analysis on vital signs*, the baseline is defined as *the pre-dose measurement* at Week 24.

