2.1.2.1 Visit windows during core and extension treatment periods

Table 2-1 Visit windows for MRI

Visit-window	Start day	Target day	End day
Week 12	1	84	98
Week 16	99	112	126
Week 20	127	140	154
Week 24 (Cut-off 1)	155	168	182
Week 36	183	252	294
Week 48	295	336	378

Day counts are relative to the first date of study drug in the Core part.

Table 2-2 Visit windows for [REDACTED] EDSS

Visit-window	Start day	Target day	End day
Week 12	1	84	126
Week 24 (Cut-off 1)	127	168	210
Week 36	211	252	294
Week 48	295	336	378
Week 60	379	420	462

Visit-window	Start day	Target day	End day
Week 72	463	504	546
Week x*	x*7-42+1	x*7	x*7+42

*if study goes beyond Week 72, every 12 weeks the same assessments on Week 60 and Week 72 will be performed. X will be a multiple of 12 weeks from Week 84 and beyond.
Day counts are relative to the first date of study drug in the Core part.

Table 2-3 Visit windows for routine lab (including urine), ADA, and Total IgM, IgG levels

Visit-window	Start day	Target day	End day
Week 4	1	28	56
Week 12	57	84	126
Week 24 (Cut-off 1)	127	168	182
Week 28	183	196	224
Week 36	225	252	294
Week 48	295	336	378
Week 60	379	420	462
Week 72	463	504	546
Week x*	x*7-42+1	x*7	x*7+42

*if study goes beyond Week 72, every 12 weeks the same assessments on Week 60 and Week 72 will be performed. X will be a multiple of 12 weeks from Week 84 and beyond.
Day counts are relative to the first date of study drug in the Core part for Cut-off 1 analysis, or the first date of ofatumumab for Cut-off 2 and final analysis.

[figure not shown]

Table 2-5 Visit windows for B-cell counts and T-cell counts: Cut-off 1 analysis

Visit-window	Start day	Target day	End day
Day 2	--	2	--
Day 5	3	5	--
Day 7	6	7	10
Day 14	11	14	21

Visit-window	Start day	Target day	End day
Week 4	22	28	56
Week 12	57	84	126
Week 24 (Cut-off 1)	127	168	182

Day counts are relative to the first date of study drug in the Core part.

Table 2-6 Visit windows for B-cell and T-cell counts: Cut-off 2 and final analysis

Visit-window	Start day	Target day	End day
Week 4	1	28	56
Week 12	57	84	126
Week 24	127	168	210
Week 36	211	252	294
Week 48	295	336	378
Week 60	379	420	462
Week 72	463	504	546
Week x*	$x * 7 - 42 + 1$	$x * 7$	$x * 7 + 42$

*if study goes beyond Week 72, every 12 weeks the same assessments on Week 60 and Week 72 will be performed. X will be a multiple of 12 weeks from Week 84 and beyond.

Day counts are relative to the first date of ofatumumab.

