2.7.2 Statistical hypothesis, model, and method of analysis

Number of new or enlarging T2 lesions on MRI scans

Analysis of the number of new or enlarging T2 lesions will be done based on the FAS using a negative binomial regression model with log-link. The number of new or enlarging T2 lesions on the last available MRI scan relative to baseline will be used as the response variable, and the natural log of the time (in years) of the MRI-assessment from the baseline/Screening scan will serve as the offset variable to adjust for the various lengths of follow-up times between patients in this study. The model will include treatment, region (Japan or other countries), baseline number of Gd-enhancing T1 lesions (0 or ≥ 1) as factors, and baseline volume of T2 lesions as continuous covariates.

The number of new or enlarging T2 lesions per year will be estimated by treatment with 95% confidence interval. The between treatment effect will be calculated as rate-ratio (ofatumumab/placebo) with 95% confidence interval and p-value. In addition, the relative reduction in the number of new or enlarging T2 lesions per year will be computed as one (1) minus the rate-ratio and expressed as a percentage.

The number of new or enlarging T2 lesions on MRI scans will be summarized descriptively by visit-window and treatment group.

The above summary analyses will be performed for both Cut-off 1 analysis and Cut-off 2 analysis ([Section 2.14](#)).

Annualized relapse rate (ARR)

Annualized relapse rate (ARR) is defined as the number of confirmed MS relapses in a year. Analysis of ARR will be done based on the FAS, using a negative binomial regression model with log-link. The model will include the number of confirmed relapses observed from each patient as the response variable, each patient's natural log of time in study (years) as the offset variable, and treatment, region (Japan or other countries), baseline number of Gd-enhancing T1 lesions (0 or ≥ 1) as factors, and number of relapses in previous year and baseline EDSS as covariates.

In the case where the above model does not converge or has other statistical limitations, a simpler model with only the offset variables, treatment and region (Japan or other countries) as factors will be fit to the data.

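### SAP 2.15 (descriptive, Cut-off 2): the T2 switch-effect rate up to Week 24 lacks a workable count reference and is timed from first dose, so counting from the baseline/Screening scan overstates it by (mean scan-to-dose gap − 1)/168

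*SAP*

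**What the plan says.** SAP 2.15 describes what happens when placebo patients switch to ofatumumab. For T2 lesions it pools total lesions over total time of MRI assessment, and this annualized rate "will be calculated by treatment and study period (up to Week 24, or thereafter").

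- **Count.** One reference is stated for the whole calculation: each patient's "number of new or enlarging T2 lesions will be relative to Week 24".
- **Time, first period.** "For the period up to Week 24, the time of MRI assessment will be defined as" the Week 24 visit date minus the first Core dose date, plus 1, divided by 365.25.
- **Time, second period.** Week 48 visit date minus Week 24 visit date, divided by 365.25. "If Week 48 visit is not available, the time of MRI assessment will be defined as" the last visit date up to Week 48 minus the Week 24 visit date, on the same scale.

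The T2 model in SAP 2.7.2 is built differently. It counts lesions on the last available scan relative to baseline, and "the natural log of the time (in years) of the MRI-assessment from the baseline/Screening scan will serve as the offset variable". For efficacy at Cut-off 2, SAP 2.1.1 says that "baseline is defined as the last non-missing result before or on the first date of study drug".

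Protocol Table 6-1 schedules one pre-dose MRI, at Screening (Day −45 to Day −8), and none at Baseline. Protocol 9.9.1 takes baseline Gd-lesion status for stratification from the screening scan.

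**The concern.** A lesion is new or enlarging on a later scan compared with an earlier one. No scan at or before Week 24 can show lesions that are new relative to Week 24, so the stated count reference cannot serve the first period and the programmer has to supply another. The obvious choice is the baseline scan, which by schedule is the Screening scan. The denominator of 2.15 nevertheless starts at first dose. Lesions that arose between the scan and first dose enter the numerator, but the days in which they arose are left out of the denominator.

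The period after Week 24 has no such gap by design: count and time both start at Week 24. The error therefore raises only the before-switch rate, and the fall in switchers, which is what this section sets out to show, looks larger than it is. SAP 1.1 says that the Cut-off 2 analysis will support registration in Japan.

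**Working it through.** The documents give no numerical result for this rate, so there is no figure to reproduce. The check is on the definitions.

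**Inputs**
- Week 24 MRI target day: 168 (SAP Table 2-1, "Visit windows for MRI").
- Day numbering: first dose is Day 1 and "there is no Study Day 0" (SAP 2.1.1). Day 168 is therefore first dose + 167 days, and Day −g is g days before first dose.
- Scheduled gap g from pre-dose scan to first dose: 8 to 45 days (Protocol Table 6-1). If the scan were repeated in the Baseline section: 0 to 7 days.
- Assumption: the Week 24 scan and visit both fall on Day 168.

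**Formula.** Scan-to-scan time is 167 + g days. The 2.15 denominator is 167 + 1 = 168 days. The rate is a ratio of totals and the lesion total L is the same under either denominator. For n patients:

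[L/(168n)] ÷ [L/Σ(167 + gᵢ)] = (167 + mean g)/168

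The excess over the scan-to-scan rate is (mean g − 1)/168, whatever the lesion counts.

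| Mean gap (days) | Ratio | Excess |
|---|---|---|
| 0 (Baseline section) | 167/168 | −0.6% |
| 7 (Baseline section) | 174/168 | 3.6% |
| 8 (all scans on Day −8) | 175/168 | 4.2% |
| 26.5 (assumed, mid-window) | 193.5/168 | 15.2% |
| 45 (all scans on Day −45) | 212/168 | 26.2% |

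Moving the Week 24 visit to Day 161 or 175, with excess (d − 1 + g)/d − 1, changes little: 4.3% or 4.0% at g = 8, and 27.3% or 25.1% at g = 45.

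A simulation of 20 placebo patients with overdispersed counts and Week 24 visits spread over Days 161–175 agreed. It gave 4.3% (all gaps 8), 15.0% (gaps uniform on 8–45), 26.3% (all gaps 45) and 1.8% (gaps uniform on 0–7). With scan-to-scan time as denominator the excess was zero within ±0.3%.

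**Effect on the before/after fall in switchers.** Assume a constant untreated lesion rate and matched count and time after Week 24. A true reduction R then appears as 1 − (1 − R) × 168/(167 + g). The factor 168/(167 + g) is 0.960, 0.868 and 0.792 at g = 8, 26.5 and 45.

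| True reduction (assumed) | g = 8 | g = 26.5 | g = 45 |
|---|---|---|---|
| 0% | 4.0% | 13.2% | 20.8% |
| 60% | 61.6% | 65.3% | 68.3% |
| 72% | 73.1% | 75.7% | 77.8% |
| 90% | 90.4% | 91.3% | 92.1% |

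The 60% and 72% are illustrative. They are the ends of the between-arm T2 result over Weeks 0–12 that Protocol 1.1 reports for the earlier subcutaneous study at other doses. The 90% is a further assumption.

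**Ofatumumab arm.** The excess over the scan-to-scan rate is the same expression. The excess over the on-drug rate is larger, because untreated pre-dose lesions are added to a lower rate. With an assumed on-drug rate half the untreated rate and g = 26.5, it is (83.5 + 26.5)/84 − 1 = 31%. The table of excesses should not be read as distortion of the on-drug rate in that arm.

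**The case against.** The strongest reply is that the gap is one of wording. SAP 2.7.2 and 2.1.1 already supply a baseline reference, and 2.15 can be read as re-referencing only the period after Week 24. That is fair. A reader might infer that the plan has no T2 reference for the first period anywhere; the documents do not support that, and the defect lies in the visible text of 2.15. But this reading is the one that produces the mismatch, because the first-dose denominator remains. Adding up counts over successive scans does not avoid it either, since the first interval still begins at the Screening scan.

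SAP 2.5.2 and 2.7.2 send Cut-off 2 analyses to a Section 2.14 that is not visible in the public text, so nothing can be said about its content. Section 2.15 does, however, set its own denominator for this calculation.

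It is tempting to quote 26% as the size of the bias. The documents do not support that: 4% and 26% need every patient at a window edge, and the mean gap is not given. The Protocol 4.2 closing note allows repeat assessments within the Screening or Baseline window, and Protocol 6.4.3 asks for faulty scans to be repeated, so some gaps may be shorter.

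The before/after figures also rest on a constant untreated rate. That is doubtful, because inclusion criterion 5 requires recent MRI activity and lets the Screening scan supply it. This weakens the second table but not the ratio (167 + mean g)/168.

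Finally, a reader might infer that the T2 evidence for registration is compromised. It is not: the registration statement covers the whole Cut-off 2 analysis, 2.15 contains no test, and the 2.7.2 model already times from the scan.

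**Conclusion.** The point holds for one descriptive rate. On the natural reading, the T2 rate up to Week 24 is too high relative to scan-to-scan time: about 15% at an assumed mid-window gap, within the limits tabulated above. The size depends on counting from the baseline/Screening scan and on a Week 24 scan near Day 168.

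The error favours a larger apparent switch effect. It matters most when the true change is small, and would not reverse a large one. The between-arm ratio up to Week 24 is unchanged if mean gaps are alike in the two arms.

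After Week 24 a smaller mismatch is possible. A reader might infer that it affects only patients without a Week 48 visit. The documents do not support that limit: 2.15 uses visit dates for everyone, and Protocol 6.4.3 lets scans be repeated or moved around steroid treatment, so it can arise for any patient whose last scan date differs from the visit date used. Its size cannot be computed from the documents.

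The primary endpoint and the 2.7.2 model are unaffected. Low-to-moderate priority.

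**What to change.** In SAP 2.15, name the reference scan for each period and use scan dates:

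- **Up to Week 24:** lesions on the Week 24 scan relative to the baseline/Screening scan, divided by (Week 24 scan date − baseline/Screening scan date).
- **After Week 24:** lesions on the last scan up to Week 48 relative to the Week 24 scan, divided by (last scan date − Week 24 scan date). Patients with no scan after Week 24 contribute neither lesions nor time.

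Add a note that the rate up to Week 24 includes a short untreated pre-dose interval in both arms, and that the before/after comparison remains descriptive. The change aligns count with time and matches 2.7.2; it does not remove the effect of selecting patients with recent MRI activity.

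The cost is SAP wording and programming. No new data are needed, because the 2.7.2 model already requires MRI assessment times. If the Cut-off 2 table has been produced, state which reference scan was programmed and rerun that table.
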